12.2.7 Safety Analysis(es)

Safety variables will be summarized on the safety population.

Exposure to study drug (number of applications, total weight of gel used) will be summarized by treatment group.

Treatment Emergent adverse events (TEAE, i.e. AEs that start or worsen after first study treatment administration) will be summarized by presenting, for each treatment group, the number and percentage of subjects having any TEAE, any TEAE in each MedDRA primary System Organ Class (SOC) and having each individual TEAE (using MedDRA preferred term). This will be done separately for all TEAEs and for TEAEs that are suspected to be drug-related. All TEAEs will also be tabulated in corresponding fashion by severity. Any other information collected (e.g. action taken, duration, outcome, seriousness) will be listed as appropriate.

All adverse events (prior to treatment and treatment emergent) will be listed.

Chemistry and hematology results at Visit 1 and at Visit 4 will be summarized by the mean, standard deviation, median, minimum and maximum values in each treatment group. Shift tables (between Visit 1 and Visit 4) will also be presented. Laboratory normal ranges and all laboratory test results will be listed.

Vital signs (systolic and diastolic blood pressure, pulse rate, respiratory rate) recorded at Visit 4 and changes in vital signs from Visit 1 (baseline) to Visit 4 will be summarized by the mean, standard deviation, median, minimum and maximum values in each treatment group. Vital signs at each assessment will also be listed.

12.2.8 Other Analysis(es)

Not applicable.

12.2.9 Handling of Dropouts and Missing Data

Multiple imputation using a simulation-based statistical technique for handling missing data as proposed by [Rubin, 1987] will be used. Multiple imputation will consist of three steps:

1. Imputation step. Missing values will be identified and replaced by a random sample of plausible values imputations (completed datasets). Under assumption of monotone missingness an imputation model with regression baseline parameters will be applied. Five imputed datasets have traditionally been suggested to be sufficient on theoretical grounds, but 50 datasets seem preferable and will be used to reduce sampling variability from the imputation process.

2. Completed-data analysis (estimation) step. The desired analysis will be performed separately for each dataset generated during the imputation step, following the ANCOVA method described in section 12.2.5.

3. Pooling step. The results obtained from each completed-data analysis will be combined into a single multiple-imputation result.

A sensitivity analysis will also be performed with no imputations for missing data and using a repeated measure mixed effect model with subject as random, and with center, treatment and timepoint (Day 3, 5 and 8) as factors and baseline value as a covariate. The treatment differences and two-sided 95% CIs for the primary end-point will be estimated for the PP and mITT analysis populations.

No imputation is planned for missing diary card pain intensity and relief assessments.

GlaxoSmithKline Consumer Healthcare Confidential Template Version Effective: 18-May-18 (CCR #11475) Page **55** of **64**

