12.2.5 Primary Analysis(es)

The primary efficacy endpoint will be change from baseline in POM on Day 5 of treatment as assessed by a 100 mm VAS scale.

The following primary non-inferiority hypothesis will be tested for DDEA 2.32% vs DDEA 1.16%:

The null hypothesis is Diclofenac 2.32% DDEA Gel administered BID is inferior to Diclofenac 1.16% DDEA gel administered QID with the alternative hypothesis being Diclofenac 2.32% DDEA Gel administered BID is non-inferior to Diclofenac 1.16% DDEA gel administered QID.

Diclofenac 2.32% DDEA Gel administered BID will be declared non-inferior to Diclofenac 1.16% DDEA gel administered QID if the upper limit of the two-sided 95% confidence interval of the difference between their mean changes from baseline VAS POM responses is less than the established margin of 13 mm.

The primary analysis will be based on an analysis of covariance (ANCOVA) with treatment and center as factors and baseline value as a covariate to estimate the treatment difference twosided 95% confidence interval for the primary endpoint to assess non-inferiority, using the per protocol and mITT analysis populations.

Evidence of a treatment-by-center interaction will be assessed by adding a factor for this interaction in a separate additional analysis model of the primary endpoint. If there is evidence of an interaction (p<0.05), then the primary endpoint outcome will also be summarized by center for further investigation and assessment

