#### 4.5.1.3 Supportive Analyses

To assess the treatment-by-center interaction an additional analysis will be performed for the primary endpoint on mITT population as following, where change from baseline on POM will be analysed using ANCOVA model with treatment, center as fixed factor, baseline POM as covariate and treatment-by-center as interaction (PPD)
 If there is evidence of an significant interaction (p<0.05) effect, then the primary endpoint outcome will also be summarized by center for further investigation and assessment.

GlaxoSmithKline Consumer Healthcare Confidential

Page 20 of 36

Reference SAS code is given in APPENDIX 4:

- 2. Sensitivity analysis will be perfomed on POM for compliance category -good. For good category greater than or equal to 80% compliance will be considered for both in application and amount of gel used for this sensitivity analysis. The sensitivity analysis for the primary endpoint will be dispayed in the tables (**PPD**).
- 3. The primary efficacy endpoint will be analyzed using ANCOVA model on ITT population using imputed data.
- 4. The Change from baseline on POM will be analyzed using Mixed Model Repeated Measure (MMRM) with multiple imputation (day 3,5,8) model with treatment, center as fixed factor, baseline POM as covariate and visit as repeated measure; using ITT population.
- 5. Same as above mentioned point 3 without imputed data, ie, observed data.
- 6. Same as above point 3 using PP population.
- 7. Same as above point 4 using PP population.

Early discontinued subjects data due to any reason- will be analyzed in this section using imputation.

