## 4.6 Analysis of Secondary Objectives

## 4.6.1 Efficacy (Secondary)

All the secondary endpoints POM at day 3 and 8, Karlsson score, tenderness, swelling and diary assessments (SPID and TOTPAR) will be analyzed using an ANCOVA model with treatment and center as fixed effect, baseline assessment for the corresponding endpoints as covariate. Treatment differences and two-sided 95% CI will be presented.

The secondary efficacy analyses will be performed and also be listed on mITT and PP population.

- Change from baseline of POM (CRF page: Pain on Movement; VAS score will be obtained from VASSCRL) on VAS on days 3 and 8 respectively (PPD).
- Tenderness measured by pressure algometry on days 3, 5 and 8 which will be analysed using change from baseline and difference between the measurement in injured area (CRF page: Tenderness; measurement for study ankle : QS\_INJA) and contralateral area (CRF page: Tenderness; measurement for study ankle : QS\_CLTA) (**PPD**)...
- Change from baseline Ankle Joint Function (Karlsson Scoring Scale; CRF page: Ankle Joint Function: Variable : Total Score KSSTS) on days 3, 5 and 8 (PPD)...
- Circumference measurement of swelling on days 3, 5 8 which will be analysed using change from baseline in circumference of affected ankle and comparison to non-affected ankle by Figure of Eight method (CRF Page:Ankle swelling; Variables: FOEMINSC and FOEMCASC respectively.) (PPD ;)..
- Pain Intensity and Pain Relief (CRF Page: Subject Diary(Day 1/5) ; variables will used to calculate the Pain Intensity and Pain Relief are DPI and DPR respectively for each timepoint (DSTMPT))
- Pain Intensity (PPD
  - Pain intensity will be analysed based on the Sum of Pain Intensity Difference (SPID). SPID is defined as from 0 -24 hours post first dose corresponding to day 1 and from 0-24 hours post first dose corresponding to day 5.
  - SPIDt=>PIDt(timet-timet-1)(h), where, PIDt=pain intensity score (DPI from CRF page corresponding to day); timet=time in hours post first dose

GlaxoSmithKline Consumer Healthcare Confidential

Page 23 of 36

211206

Statistical Reporting and Analysis plan Draft V2.0 20JAN2021

- Pain Relief (**PPD** 
  - Pain relief will be analysed based on the Total Pain Relief (TOTPAR). TOTPAR is defined as from 0-24 hours post first dose corresponding to day 1 and from 0-24 hours post first dose corresponding to day 5.

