#### SAS code for Supportive Analysis

\*The variance-covariance matrix structure will be selected based on data

\*The variance-covariance matrix structure will be selected based on data

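### The repeated-measures sensitivity model for the Day 5 endpoint lists no treatment-by-visit term, so as written it returns one difference pooled over Days 3, 5 and 8

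*Protocol*

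**What the plan says.** The endpoint is tied to a single visit. Protocol 12.2.5 states: "The primary efficacy endpoint will be change from baseline in POM on Day 5 of treatment".

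Protocol 12.2.9 then describes a sensitivity analysis without imputation, "using a repeated measure mixed effect model with subject as random, and with center, treatment and timepoint (Day 3, 5 and 8) as factors", with baseline as covariate. It names the target of that model: "The treatment differences and two-sided 95% CIs for the primary end-point will be estimated for the PP and mITT analysis populations".

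SAP 4.5.1.3 item 4 gives the SAP's version, run on the ITT set: "MMRM) with multiple imputation (day 3,5,8) model with treatment, center as fixed factor, baseline POM as covariate and visit as repeated measure". Item 7 repeats it: "Same as above point 4 using PP population". SAP section 5, which lists departures from the protocol, records no change to the terms of this model.

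The only interaction named in either document is treatment-by-center, in a separate ANCOVA. For the supportive models, all that can be read in SAP Appendix 4 is a comment on the covariance: "The variance-covariance matrix structure will be selected based on data".

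**The concern.** The model is meant to show whether the Day 5 result holds under a different treatment of missing data. A model with treatment and timepoint as main effects only forces the treatment difference to be the same on Days 3, 5 and 8, and no Day 5 contrast can be taken from it. If the true difference varies by visit, the sensitivity analysis changes two things at once: how missing data are handled and what is being estimated. A gap from the primary ANCOVA could then come from either source, and agreement could be falsely reassuring. The pooled interval is also narrower than a Day 5 interval, so it suggests more precision about Day 5 than the trial has.

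**Working it through.** **Inputs from the documents** (Protocol 12.1, SAP 1.4): SD 22 mm, 120 evaluable per arm, margin 13 mm, assumed true difference 5 mm, two-sided 95% CI.

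**Assumptions, because the documents give no figures:** the visit-specific true differences; a between-visit correlation ρ of 0.3, 0.5 or 0.7; the same SD at each visit; complete data.

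**The plan's own figure.** n per arm = 2 × 22² × (1.96 + 0.8416)² / (13 − 5)² = 968 × 7.849 / 64 = 118.7, so 119, against the stated 120. The SE of a Day 5 difference is 22 × √(2/120) = 2.84 mm. Power at 120 per arm is Φ(8/2.84 − 1.96) = 0.804. The sample size reproduces and is for a single-visit comparison.

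**What the listed terms estimate.** With balanced complete data, the single treatment coefficient is a weighted mean of the three visit differences, with R the correlation matrix over visits:

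- weights = R⁻¹1 / (1′R⁻¹1)
- SE = 2.84 × √(1 / 1′R⁻¹1)
- P(upper limit < 13) = Φ((13 − estimate)/SE − 1.96)

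*Random subject (compound symmetry), as in the protocol.* Each visit has weight 1/3 whatever ρ is. SE = 2.84 × √((1 + 2ρ)/3) = 2.07, 2.32 and 2.54 for ρ = 0.3, 0.5 and 0.7.

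*AR(1) by visit order, one structure the SAP's open choice could lead to.* The Day 5 weight is (1 − ρ)/(3 − ρ) = 0.259, 0.200 and 0.130. SE = 2.84 × √((1 + ρ)/(3 − ρ)) = 1.97, 2.20 and 2.44.

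**Results** (three values are for ρ = 0.3 / 0.5 / 0.7):

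| True difference, Days 3/5/8 (mm) | Random subject: estimate | Random subject: P | AR(1): estimate | AR(1): P | Day 5 contrast: P |
|---|---|---|---|---|---|
| 10/13/10 | 11.0 | 0.160 / 0.136 / 0.121 | 10.78 / 10.60 / 10.39 | 0.203 / 0.192 / 0.186 | 0.025 |
| 12/13/12 | 12.33 | 0.051 / 0.047 / 0.045 | 12.26 / 12.20 / 12.13 | 0.057 / 0.055 / 0.054 | 0.025 |
| 8/5/8 | 7.0 | 0.825 / 0.735 / 0.656 | 7.22 / 7.40 / 7.61 | 0.834 / 0.721 / 0.598 | 0.804 |
| 13/13/13 or 15/13/11 | 13.0 | 0.025 | 13.0 | 0.025 | 0.025 |

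P is the probability that the 95% CI upper limit lies below 13 mm.

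**Checks by simulation and model fitting.**

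- Simulating 20,000 trials at 10/13/10 gave 0.156 / 0.136 / 0.119 (random subject), 0.198 / 0.196 / 0.186 (AR(1)) and 0.023 to 0.025 (Day 5 contrast).
- One simulated trial of 240 subjects, with assumed differences 5/13/0, had by-visit ANCOVA differences of 7.04, 13.83 and −2.56 mm. The model with the listed terms returned 6.10 mm (SE 2.43), and (7.04 + 13.83 − 2.56)/3 = 6.10. Adding treatment-by-visit gave 13.47 mm (SE 2.96) for Day 5.
- Mixed-model fits at 10/13/10 with 6,000 per arm (ρ = 0.3 and 0.7) gave 11.25 and 11.31 mm (SE 0.29 and 0.36) with the listed terms. With the interaction, the Day 5 contrast was 12.87 and 13.30 mm (SE 0.40 each).

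**The case against.** The strongest reply is that the decisive text cannot be read. The SAP refers to Appendix 4 for its code, and the code for this model is not legible, so the term may be there. The protocol also names the primary endpoint as the target and defers detail to the SAP, and many statisticians take treatment-by-visit as implied in a model of this kind. On that reading the specification is incomplete rather than wrong. Part of this stands: the SAP program cannot be faulted unseen. But the protocol enumerates its terms, and both documents spell out an interaction where they want one (treatment-by-center). A programmer following the prose would fit the additive model. If the code does contain the term, text and code disagree and the text still needs an edit.

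The second reply concerns size. No document suggests that Day 5 is worse than both neighboring visits. Smooth patterns barely move the estimate: with equal weights, 7/5/3 gives 15/3 = 5.0 mm and 8/5/3 gives 16/3 = 5.3 mm. Only two covariance structures with equal variances were examined, and AR(1) was indexed by visit order although the visits are 2 and 3 days apart. All of that is fair. The figures show what can happen, not what is expected.

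Third, safeguards exist. SAP 4.6.1 analyzes "All the secondary endpoints POM at day 3 and 8" by separate ANCOVAs, POM is summarized over time, and the multiple-imputation ANCOVA is itself a missing-data check at Day 5. These would reveal a varying effect, but they do not supply the Day 5 estimate that the repeated-measures model is said to provide.

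**Conclusion.** The concern holds for the plan as written. That the listed terms give one common treatment difference follows from the model and needs no numerical assumption. The pooled value equals the Day 5 difference only when the effect is constant over visits or the weighted visit differences happen to average to it. With incomplete data or another covariance structure the weights change, but the result is still a single value.

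The error can go either way. In the illustrations it ranges from none, through about 4.5–5.7% for 12/13/12, to 12–20% for 10/13/10, each against 2.5%. For 8/5/8 the probability is 60–83%, against 80%. These are properties of a supportive analysis with no decision rule attached and are not the trial's type I error. The point should be corrected, but it does not threaten the main conclusion.

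**What to change.** In SAP 4.5.1.3 items 4 and 7, and in Protocol 12.2.9 (or as a listed change in SAP section 5), state that visit and treatment-by-visit are fixed effects and that the reported result is the Day 5 treatment contrast with its two-sided 95% CI. Make the Appendix 4 code match. If it already contains the term, only the text changes.

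The cost is one line of text and code, with no new data. The interval becomes wider: the half-width is 1.96 × 2.84 = 5.6 mm for the Day 5 contrast, against 4.1–5.0 mm (random subject) or 3.9–4.8 mm (AR(1)) for the pooled value, under the assumptions above. The wider interval is the honest precision for Day 5.

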12.2.10 Interim Analysis

No interim analysis is planned for this study

13 STUDY GOVERNANCE CONSIDERATIONS

13.1 Quality Control

In accordance with applicable regulations including GCP, and GSK CH procedures, GSK CH or designee (i.e. third-party vendor) monitors will contact the site prior to the start of the study to review with the site staff the protocol, study requirements, and their responsibilities to satisfy regulatory, ethical, and GSK CH requirements.

When reviewing data collection procedures, the discussion will include identification, agreement and documentation of data items for which the CRF will serve as the source document.

GSK CH or designee will monitor the study and site activity to verify that the:

- Data are authentic, accurate, and complete.
- Safety and rights of subjects are being protected.
- Study is conducted in accordance with the currently approved protocol and any other study agreements, GCP, and all applicable regulatory requirements.

The extent and nature of monitoring will be described in a written monitoring plan on file at GSK CH. The investigator (or designee) agrees to allow the monitor direct access to all relevant documents and agrees to co-operate with the monitor to ensure that any problems detected in the course of these monitoring visits are resolved.

13.2 Quality Assurance

To ensure compliance with GCP and all applicable regulatory requirements, GSK CH may conduct a quality assurance assessment and/or audit of the site records, and the regulatory agencies may conduct a regulatory inspection at any time during or after completion of the study.

In the event of an assessment, audit or inspection, the investigator (and institution) must agree to grant the advisor(s), auditor(s) and inspector(s) direct access to all relevant documents and to allocate their time and the time of their staff to discuss the conduct of the study, any findings/relevant issues and to implement any corrective and/or preventative actions to address any findings/issues identified.

The investigator(s) will notify GSK CH or its agents immediately of any regulatory inspection notification in relation to the study. Furthermore, the investigator will cooperate with GSK CH or its agents to prepare the study site for the inspection and will allow GSK CH or its agent, whenever feasible, to be present during the inspection. The investigator will promptly apply copies of the inspection finding to GSK CH or its agent. Before response submission to the regulatory authority, the investigator will provide GSK CH or its agents with an opportunity to review and comment on responses to any such findings.

The sponsor will be available to help investigators prepare for an inspection.

13.3 Regulatory and Ethical Considerations

13.3.1 Institutional Review Board/ Ethics Committee

It is the responsibility of the investigator to have prospective approval of the study protocol, protocol amendments, informed consent documents, investigator brochure/safety statement (including any updates) and other relevant documents, e.g. recruitment advertisements, if applicable, from the IRB/EC. All correspondence with the IRB/EC should be retained in the investigator file. Copies of IRB/EC approvals should be forwarded to GSK CH prior to the initiation of the study, and also when subsequent amendments to the protocol are made.

The only circumstance in which an amendment may be initiated prior to IRB/EC approval is where the change is necessary to eliminate apparent immediate hazards to the subjects. In that event, the investigator must notify the IRB/EC and GSK CH in writing immediately after the implementation.

13.3.2 Ethical Conduct of the Study

The study will be conducted in accordance with legal and regulatory requirements, as well as the general principles set forth in the International Ethical Guidelines for Biomedical Research Involving Human Subjects (Council for International Organizations of Medical Sciences 2002), International Ethical Guidelines for Health-Related Research Involving Humans (Council for International Organizations of Medical Sciences, 2016), guidelines for GCP (ICH 1996 and revision 2), and the Declaration of Helsinki (World Medical Association 2013).

In addition, the study will be conducted in accordance with the protocol, the ICH guideline on GCP, and applicable local regulatory requirements and laws.

13.3.3 Subject Information and Consent

All parties will ensure protection of subject personal data and will not include subject names or other identifiable data in any reports, publications, or other disclosures, except where required by laws.

When study data are compiled for transfer to GSK CH and other authorized parties, subject names, addresses, and other identifiable data will be replaced by numerical codes based on a numbering system provided by GSK CH/CRO in order to de-identify study subjects.

The study site will maintain a confidential list of subjects who participated in the study, linking each subject's numerical code to his or her actual identity. In case of data transfer, GSK CH will maintain high standards of confidentiality and protection of subjects' personal data consistent with applicable privacy laws.

The informed consent documents must be in compliance with ICH GCP, local regulatory requirements, and legal requirements, including applicable privacy laws.

The informed consent documents used during the informed consent process must be reviewed and approved by the sponsor, approved by the IRB/EC before use, and available for inspection.

The investigator must ensure that each study subject, is fully informed about the nature and objectives of the study and possible risks associated with participation.

13.3.4 Subject Recruitment

Advertisements approved by IRBs/ECs and investigator databases may be used as recruitment procedures. Use of ethics committee approved, generic, prescreening questionnaire to assess

GlaxoSmithKline Consumer Healthcare Confidential Template Version Effective: 18-May-18 (CCR #11475) Page **57** of **64**

basic subject characteristics to determine general eligibility for this study is allowed. This generic questionnaire may be used by sites as a phone script and/or to review internal databases to identify subjects.

GSK CH will have an opportunity to review and approve the content of any study recruitment materials directed to potential study subjects before such materials are used.

13.3.5 Reporting of Safety Issues and Serious Breaches of the Protocol or ICH GCP

Within GSK CH a serious breach is defined as a breach likely to affect to a significant degree the safety and rights of a subject or the reliability and robustness of the data generated in GSK CH-sponsored human subject research studies.

In the event of any prohibition or restriction imposed (i.e., clinical hold) by an applicable competent authority in any area of the world, or if the investigator is aware of any new information that might influence the evaluation of the benefits and risks of the investigational product, GSK CH should be informed immediately.

In addition, the investigator will inform GSK CH immediately of any urgent safety measures taken by the investigator to protect the study subjects against any immediate hazard, and of any serious breaches of this protocol or of ICH GCP that the investigator becomes aware of.

